Because the toxicity of Nivolumab combined with SBRT is unclear, we have included an interim toxicity analysis for Arm 2 to occur after the first 20 patients have been randomized to this arm. Using data from recently reported early phase trials of Nivolumab in NSCLC, we view 14% as an acceptable rate of acute (within 3 months of study initiation) \geq Grade 3 treatment-related adverse events; an unacceptable rate of acute \geq Grade 3 treatment-related adverse events is 30%. If more than 5 (e.g. 6 or more) of the first 20 patients experience an acute \geq Grade 3 treatment-related adverse event, the trial will be stopped early. If the true toxicity rate is 30%, the above boundary assures a 58% probability of stopping the trial at interim analysis; if the true toxicity rate is 40%, there is an 87% chance of stopping the trial early. If the true toxicity rate is 14%, the above boundary has only a 5% probability of stopping the trial early. Of note, for radiation dermatitis, only Grade 4 treatment-related events will be included in the interim analysis of toxicity.

Study mandated follow-up for tumor assessment will conclude 96 weeks after the final patient is enrolled.

The primary endpoint of the trial is the ORR as defined by RECIST 1.1 criteria. Analysis of ORR will occur 96 weeks after randomization of the final subject.

The maximal total duration of the study from start of randomization to final analysis of ORR is expected to be 44 months, assuming an accrual of 3 patients per month. Sample size estimate is 60 patients.

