9.2 Intervention: SBRT

9.2.1 Target Selection

- A single target lesion will be selected.
- The lesion must be safely amenable to irradiation in the judgment of the treating radiation oncologist; approval of PI is not required.
- Lesions must be located in one of the following eight locations:
 - Central Lung Tumors: GTVs within 2cm of the proximal bronchial tree (carina, right and left main bronchia, right and left upper lobe bronchi, intermedius bronchus, right middle lobe bronchus, lingular bronchus right and left lower lobe bronchi.
 - Lung Peripheral: metastases within the lung parenchyma with GTV outside of the proximal bronchial tree as described above.
 - Mediastinal Lymph Nodes: GTV arising within the anatomic space between the lungs, above the diaphragm, and below the thoracic inlet at the level of the top of the sterna notch.
 - Head and Neck: GTV occurring within cervical lymph node levels I-VI and/or retropharyngeal spaces, oral cavity, oropharynx, nasopharynx, hypopharynx, para-nasal sinuses, nasal cavity, and parotid gland/space.
 - Liver: GTV arising within the liver.
 - Spine: metastases will be assigned to the spinal/paraspinal site if the GTV arises within the vertebral bodies expanded by 1cm.
 - Osseous: GTV arising within an osseous structure, part of the axial skeleton, not included in the spinal definition.
 - Abdominal-Pelvic: GTV arising within the anatomic space defined by the diaphragm superiorly, the genitourinary diaphragm inferiorly include the peritoneal and retroperitoneal spaces, not including liver, osseous, or spinal metastases.
- While no specific size constraint exists, the treating radiation oncologist must have a reasonable expectation that the dose constraints outlined in the appendix will be met; if, during planning, dose constraints to outlined normal tissue structures are exceeded, the treating radiation oncologist must receive permission of the study PI ([name]) prior to proceeding with treatment. If permission is not obtained, the patient will be withdrawn from the study.
- In instances where there is a metastatic or recurrent lesion that is either causing symptoms or on the precipice of doing so, the treating radiation oncologist should select this lesion for irradiation.
- Every effort should be made to choose a target lesion outside of a previously irradiated site. However, the treated lesion can be a lesion that was previously

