All tr-AEs will be tabulated and summarized. The cumulative incidence of all tr-AEs and Grade 3+ tr-AEs, etc., will be compared between the two arms by using Gray's test. For this analysis all randomized subjects who received at least one dose of study drug will be included.

The questions on the HRQOL will be scaled and scored using the recommended EORTC Quality of Life Group procedures. Raw scores will be transformed using a linear scale ranging from 0 to 100, with a higher score representing a higher level of functioning or a higher level of symptoms. Wilcoxon rank sum tests will be conducted to compare the scores across the two arms and longitudinal plots will be made to visually examine the pattern of change of scores at each specified time point. If appropriate, an exploratory linear mixed model will also be used to incorporate correlations among various time points, and include additional variables such as interaction between treatment and number of assessments, site of the primary tumor, baseline score, and performance status.

Because the toxicity of Nivolumab combined with SBRT is unclear, we will utilize an interim stopping rule for Arm 2 based on the first 20 randomized to this arm to protect later patients from unacceptably high toxicity rate. Using data from recently reported early phase trials of Nivolumab in NSCLC, we view 14% as an acceptable rate of acute (within 3 months of study initiation) \geq Grade 3 treatment-related adverse events; an unacceptable rate of acute \geq Grade 3 treatment-related adverse events is 30%. If more than 5 (e.g. 6 or more) of the first 20 patients experience an acute \geq Grade 3 treatment-related adverse event, the trial will be stopped early. If the true toxicity rate is 30%, the above boundary assures a 58% probability of stopping the trial at interim analysis; if the true toxicity rate is 40%, there is an 87% chance of stopping the trial early. If the true toxicity rate is 14%, the above boundary has only a 5% probability of stopping the trial early. Of note, for radiation dermatitis, only Grade 4 treatment-related adverse events will be included in the interim analysis.

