For the exploratory objectives, all lab measurements will be summarized and descriptive statistics will be provided. When correlation between lab measurements and treatment outcomes are of interest, Wilcoxon rank sum tests will be conducted to examine the difference between responders and non-responders within each arm. An exploratory multivariate logistic regression analysis to determine whether, once adjusted for relevant clinical covariates and treatment arm, tumor PD-L1 or serum immunophenotypic changes predict for response to Nivolumab.

To clarify we define population for the above analyses

- Randomized subjects for ORR analysis: all enrolled subjects who were randomized and provided at least 6 months of follow-up after treatment initiation. This is the dataset for the primary objective and irORR.
- All randomized subjects: all enrolled subjects who were randomized. This is the dataset for baseline demographics and time-to-event endpoints (PFS, OS).
- Treated subjects: all randomized subjects who received at least one dose of study drug. This is the dataset for safety evaluation. For instance, if a subject receives a single dose of Nivolumab but withdraws from study prior to the first dose of radiation, that subject will be considered treated.
- Biomarker Subjects: all randomized subjects with available biomarker data.
- PRO subjects: all subjects with available Patient Reported Outcomes (PRO) data.

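### The Arm 2 toxicity stopping rule counts the first 20 randomised, whether or not they received SBRT, so for the combination's toxicity the stated 58% and 87% stopping probabilities are upper limits

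*Combined protocol and SAP*

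**What the plan says.** Two places define the interim look, and both count randomised patients. Section 4.2 (Design) describes an "interim toxicity analysis for Arm 2 to occur after the first 20 patients have been randomized to this arm". Section 14.0 (Biostatistics, under the heading numbered 11.1) says "we will utilize an interim stopping rule for Arm 2 based on the first 20 randomized to this arm". The boundary reads "If more than 5 (e.g. 6 or more) of the first 20 patients experience an acute" Grade 3 or higher treatment-related event. The benchmark is given as "we view 14% as an acceptable rate of acute (within 3 months of study initiation"), and 30% is the unacceptable rate. The stated performance is "If the true toxicity rate is 30%, the above boundary assures a 58% probability of stopping the trial at interim analysis" and "if the true toxicity rate is 40%, there is an 87% chance of stopping the trial early", with 5% at a true rate of 14%.

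Other sections show how an Arm 2 patient can occupy one of the 20 places without receiving SBRT:

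- Section 9.1 places CT simulation after randomisation. It allows the first fraction to be as late as study day 14, whereas nivolumab starts on day 1.
- Section 9.2.1 (Target Selection) deals with plans that exceed normal-tissue constraints and need the principal investigator's agreement: "If permission is not obtained, the patient will be withdrawn from the study". Exceeding the re-irradiation constraints also leads to withdrawal.
- The population definitions in section 14.0 give this case as their example for the safety dataset, in a sentence that ends by classing the patient as treated: "if a subject receives a single dose of Nivolumab but withdraws from study prior to the first dose of radiation, that subject will be considered".

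The only replacement rule, in section 14.0, covers loss to follow-up before 6 months. It serves the response endpoint and is not linked to the toxicity rule.

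**The concern.** Both sections justify the rule by the unknown toxicity of nivolumab given with SBRT. A patient who receives nivolumab alone, or nothing, tells us little about that, but still uses up one of the 20 places. If such patients have fewer Grade 3 or higher events than patients given both treatments, each of them makes it harder to reach six events. The rule is then less likely to stop a toxic combination than the quoted figures suggest, and the error always runs in that direction. At the rate the protocol calls unacceptable, the rule starts at only 58%, so there is little to spare.

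**Working it through.** **Inputs from the documents.** n = 20 and stop at 6 or more; true rates 14%, 30% and 40% (section 14.0). Accrual is 3 patients per month, randomised 1:1 (section 14.0), which is 1.5 per month to Arm 2.

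**Assumed inputs.** The documents do not give k, the number of the 20 who never receive SBRT, so k = 1 and k = 2 are shown. The event rate q in those patients is set to 0 (no events) or to 0.14 (the protocol's acceptable rate, drawn from nivolumab trials).

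**Step 1: reproduce the plan's figures.** With all 20 exposed, X ~ Binomial(20, p), and P(X ≥ 6) is:

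- p = 0.14: 0.0507 (stated 5%)
- p = 0.30: 0.5836 (stated 58%)
- p = 0.40: 0.8744 (stated 87%)

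All three agree.

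**Step 2: let k of the 20 miss SBRT.** The event count is Binomial(20 − k, p) + Binomial(k, q), so

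P(stop) = Σ over j = 0..k of C(k, j) q^j (1 − q)^(k − j) × P[Binomial(20 − k, p) ≥ 6 − j].

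Worked example with k = 2, p = 0.30, q = 0.14. The tails of Binomial(18, 0.30) at 6, 5 and 4 are 0.4656, 0.6673 and 0.8354. Then 0.7396 × 0.4656 + 0.2408 × 0.6673 + 0.0196 × 0.8354 = 0.3444 + 0.1607 + 0.0164 = 0.521. With q = 0 only the first tail remains, giving 0.466.

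| Patients of 20 without SBRT | 30% rate, q = 0 | 30% rate, q = 0.14 | 40% rate, q = 0 | 40% rate, q = 0.14 |
|---|---|---|---|---|
| 0 | 58.4% | 58.4% | 87.4% | 87.4% |
| 1 | 52.6% | 55.3% | 83.7% | 85.0% |
| 2 | 46.6% | 52.1% | 79.1% | 82.2% |

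The loss with one patient is about 3 to 6 points at 30% and 2 to 4 points at 40%. With two it is about 6 to 12 points and 5 to 8 points. At a true rate of 14% the probability stays at 5.1% when q = 0.14, and falls to 4.0% (k = 1) or 3.1% (k = 2) when q = 0.

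**Step 3: effect of the proposed fix.** Suppose 10% miss SBRT, 14% of those have a qualifying event and keep their place, and the rest are replaced. The event rate per filled place at a true rate of 14% is (0.90 × 0.14 + 0.10 × 0.14) / (0.90 + 0.10 × 0.14) = 0.140 / 0.914 = 0.153. P[Binomial(20, 0.153) ≥ 6] is then 0.073, against 0.051 when nobody misses SBRT.

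**Step 4: delay.** Replacing two patients takes 2 / 1.5 = 1.3 months of Arm 2 accrual.

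**The case against.** The strongest reply is that nothing in the plan is miscalculated. The rule is described as one for Arm 2, and the true toxicity rate is never defined as the rate among patients given SBRT. Read as the rate per patient randomised to Arm 2, 58% and 87% are exact. They are also exact if all 20 receive SBRT. This stands: a reader might infer that the quoted probabilities are wrong or cannot be attained, and the documents do not support that.

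Second, missed SBRT should be uncommon. Section 6.2 requires a lesion that the radiation oncologist judges can be irradiated safely and will probably meet the planning criteria, and it asks for insurance approval of SBRT before randomisation. For a first irradiation, exceeding a constraint leads to withdrawal only if the principal investigator's permission is not obtained. This also stands, and it argues for small k, though not for k = 0. It is tempting to take the 10% drop-out in section 14.0 as the missed-SBRT rate. That figure is whole-trial drop-out, used to inflate 54 patients to 60, and a patient who drops out after SBRT was exposed.

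Third, counting a nivolumab-only patient as treated is a prespecified choice, and never-dosed patients fall outside the safety dataset. If that dataset also governs the interim rule, never-dosed patients would not count and the q = 0.14 columns are the more relevant ones. The text of the rule, however, says randomised and does not refer to that dataset.

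Fourth, the boundary is not the only protection. The institutional data and safety monitoring committee, serious-event reporting, the nivolumab delay and discontinuation criteria and the between-arm comparison of adverse events all remain. It is the only numeric toxicity stopping boundary, which is a narrower statement.

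Finally, one might want the 3-month window to start at SBRT. The 14% benchmark comes from nivolumab trials over a 3-month period. Moving the start would lengthen observation beyond that period, and no effect on stopping has been calculated. The point does not extend to the window.

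**Conclusion.** The point holds as a gap in the definition of who is counted. The rule is meant to judge the combination, its denominator does not require the combination to have been given, and the protocol describes patients for whom the two differ. For the combination's toxicity, 58% and 87% are upper limits. With one of 20 missing SBRT they become 53-55% and 84-85%; with two, 47-52% and 79-82%.

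This rests on three assumptions: the true rate is read as that of patients given both treatments, patients without SBRT have a lower event rate, and one or two of the 20 miss SBRT. The last is illustrative. If nobody misses SBRT, nothing is lost.

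**What to change.** In sections 4.2 (Design) and 14.0, define the set for the interim rule. Apply the existing boundary of 6 or more to the first 20 Arm 2 patients who received at least one nivolumab dose and at least one SBRT fraction. Replace a patient within the 20 only if that patient missed SBRT and had no qualifying event. An Arm 2 patient with a treatment-related Grade 3 or higher event after nivolumab but before SBRT still counts as an event and fills a place. Without that provision, a patient whose early toxicity prevented radiation would be removed because of the outcome, which again biases the rule toward not stopping. Replaced patients stay in the safety tables. The boundary and the window are unchanged.

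Alternatively, keep the randomised denominator, say that the true rate is per randomised patient, and restate the stopping probabilities for the combination under an assumed non-receipt rate.

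The first option costs a short addition in each of the two sections and about 1-2 months' delay in reaching the twentieth evaluable patient if two are replaced. Retaining events before SBRT also makes the rule slightly more likely to stop: about 7% rather than 5% at a true rate of 14%, under the assumptions of step 3. The second option costs only the restatement, but leaves the lower chance of stopping in place.

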- 3) Prior treatment with an anti-PD-1, anti-PD-L1, anti-PD-L2 antibody.
- 4) Prior active malignancy within the previous 3 years except for locally curable cancers such as basal or squamous skin cancer, superficial bladder, low risk prostate cancer, breast, or cervix cancer. If other prior malignancy was active within prior 3 years, enrollment requires approval of a principal investigator.
- 5) Subjects with active, known or suspected auto-immune disease. Subjects with vitiligo, type 1 diabetes mellitus, residual hypothyroidism due to autoimmune condition only requiring hormone replacement, psoriasis not requiring systemic treatment, or conditions not expected to recur in the absence of an external trigger are eligible to enroll.
- 6) Subjects with a condition requiring systemic treatment with either corticosteroids (> 10 mg daily prednisone equivalents) or other immunosuppressive medications within 14 days of study drug administration. Inhaled or topical steroids and adrenal replacement doses >10 mg daily prednisone equivalents are permitted in the absence of active autoimmune disease.

Based upon an estimated ORR of 15% in the Nivolumab alone arm in a PD-L1 unselected population and an ORR of 45% in the Nivolumab and SBRT arm, the enrollment of 54 patients will provide a one-sided alpha of 0.10 and a power of 0.80. Assuming a 10% drop-out rate, we will seek to enroll 60 patients. Patients will be randomized to the two

treatment arms in a 1:1 ratio (30 subjects in Arm 1 and 30 subjects in Arm 2). Patients will be stratified based upon viral status (HPV/EBV+ vs not). ORR will be assessed by the investigator using RECIST 1.1 criteria. Treatment with Nivolumab will continue until RECIST 1.1-defined progression, unacceptable toxicity, or withdrawal of consent. Nivolumab dose reductions will not be allowed.

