12.1.6 Baseline Documentation of "Target" and "Non-Target" Lesions

12.1.6.1 Target Lesions

When more than one measurable lesion is present at baseline all lesions up to a maximum of five lesions total representative of all involved organs should be identified as target lesions and will be recorded and measured at baseline.

Target lesions should be selected on the basis of their size, be representative of all involved organs, and should lend themselves to reproducible repeated measurements.

A sum of diameters (longest for non-nodal lesions, short axis for nodal lesions) for all target lesions will be calculated and reported as the baseline sum diameters. If lymph nodes are to be included in the sum, then as noted below, only the short axis is added into the sum. The baseline sum diameters will be used as reference to further characterize any objective tumor regression in the measurable dimension of the disease.

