12.3.1 Baseline PD-L1 Expression on Tumor Cells

Fresh biopsies will be provided for biomarker analysis if accessible and deemed safe and clinically necessary by the investigator. An archived biopsy of metastatic or loco-regionally recurrent disease obtained prior to therapy is acceptable if the fresh biopsy is not clinically indicated. If neither fresh nor archived material are available from recurrent/metastatic site, archived material from the primary disease at diagnosis is allowable with permission of PI. On-treatment biopsies are not required.

Expression of PD-L1 expression on tumor cells will be assessed using an automated immunohistochemical assay developed by BMS and Dako. PD-L1 positivity will be defined as at least 5% of tumor cells showing cell surface PD-L1 staining of any intensity in a section containing at least 100 tumor cells that could be evaluated. Expression of PD-L2 expression on tumor infiltrating lymphocytes (TILs) may also be assessed. Additional IHC studies may be conducted evaluating CD4, CD8, FOXP3, HLA Class I,

Antigen Presenting Machinery (APM), and HPV oncoproteins expression. PD-L1 IHC will be conducted by BMS (see appendix for additional information)

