14.0 BIOSTATISTICS

11.1 Primary Objective

The primary objective of this study is to compare best overall response (BOR) rate by 96 weeks as determined by the investigator using RECIST 1.1 criteria between patients receiving Nivolumab and SBRT and those receiving Nivolumab alone. BOR rate is defined as the number of patients randomized to a given arm with a best overall response of complete response (CR) or partial response (PR) of non-irradiated lesions divided by the total number of patients randomized to the given arm. In order to ascertain this endpoint, efforts will be made so that patients will be followed for 96 weeks or until progression of disease (and treatment cessation), whichever comes first.

Based upon an estimated ORR of 15% in a PD-L1 unselected population in the Nivolumab alone arm (based on data from Siewert, et al; see background) and an ORR of 45% in the Nivolumab and SBRT arm, the enrollment of 54 patients with a two-sample proportion test will provide a one-sided alpha of 0.10 and a power of 0.80. Assuming a 10% drop-out rate, we will enroll a total of 60 patients. Patients will be randomized to the two treatment arms in a 1:1 ratio. Patients will be stratified based upon viral status (virus negative versus virus positive; virus status is defined by EBV (EBER testing) or HPV (p16, HPV ISH, HPV PCR) testing). Assuming a constant enrollment of 3 subjects per month, it would take approximately 20 months to randomize 60 patients. Calculations were completed using software R 3.1.1 and EAST 6.

To ensure eligible endpoints are well defined, a minimum of 6 months of follow up after treatment initiation is required. Patients lost to follow-up prior to 6 months (24 week scan) will be replaced, regardless of response. Patients lost to follow-up between 6 months and 24 months will be included in the ORR calculation.

Secondary objectives:

OS and PFS will be evaluated by the regular survival analysis tools such as Kaplan-Meier and competing risks methods. Comparisons will be conducted between the two arms by the stratified log-rank test and Gray's test.

The DOR will be calculated from the time of response to progression or last follow up and analyzed using the Kaplan-Meier method among patients who showed response.

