16.1 DATA MANAGEMENT ISSUES

Data will be managed by a designated RSA from the Department of Radiation Oncology at MSKCC. All data will be managed in compliance with institutional policy and kept in iMedidata.

List of variables and population characteristics

- Patient demographic data (date of birth, height, weight)
- Medical history
- Concomitant medication
- Adverse events
- Laboratory Values
- Tumor Assessment Data
- Quality of Life Assessment Data
- Tumor PD-L1 status
- MDSC results

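### Section 14.0 relates biomarkers to tumour response only as responder yes/no, although graded tumour change is already measured; adding a rank analysis of percent change would recover power if the association is graded

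*Combined protocol and SAP*

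**What the plan says.** Section 2.1 lists four exploratory objectives: tumour PD-L1, blood mononuclear cell composition, soluble PD-1 and PD-L1, and (optionally) neo-antigens, each to be correlated with response. The analysis is in the closing paragraphs of section 14.0. Laboratory measurements are to be summarised, and where correlation with outcome is of interest, "Wilcoxon rank sum tests will be conducted to examine the difference between responders and non-responders within each arm". An exploratory multivariable logistic regression of response, adjusted for clinical covariates and treatment arm, follows. No other biomarker-response analysis is described, and no effect size, significance level or power is attached to these two.

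The graded outcome is collected. Section 10.1.2 schedules scans every 8 weeks to week 48 and every 12 weeks to week 96 or progression. Section 12.1.6.1 requires a sum of diameters: "The baseline sum diameters will be used as reference to further characterize any objective tumor regression in the measurable dimension of the disease". Section 12.1.7 defines a partial response as a fall of at least 30% in that sum, so percent change must be computed to apply the definition.

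For PD-L1, section 12.3.1 states that "PD-L1 positivity will be defined as at least 5% of tumor cells showing cell surface PD-L1 staining of any intensity", and the variable list in section 16.1 names "Tumor PD-L1 status".

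**The concern.** A yes/no outcome puts a 25% shrinkage and a doubling in the same group. The loss is greatest when one group is small, and the design assumptions make it small in Arm 1: "Based upon an estimated ORR of 15% in the Nivolumab alone arm in a PD-L1 unselected population" (section 4.2), with 30 patients in that arm. A responder v non-responder test there would compare about 4 or 5 patients with about 25 or 26.

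Arm 1 is the only arm that shows what predicts response to nivolumab alone. If a biomarker tracks shrinkage by degrees, the planned test would usually miss it there, and a null result would say little about the biomarker. What is at stake is the yield of the exploratory work, not the ORR comparison.

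**Working it through.** **1. The plan's own figure.** Section 14.0 takes "Based upon an estimated ORR of 15% in a PD-L1 unselected population in the Nivolumab alone arm" and "an ORR of 45% in the Nivolumab and SBRT arm", with "a one-sided alpha of 0.10 and a power of 0.80". With p1 = 0.15, p2 = 0.45 and mean 0.30:

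- n per arm = [1.2816 × √(2 × 0.30 × 0.70) + 0.8416 × √(0.15 × 0.85 + 0.45 × 0.55)]² / 0.30² = (0.8306 + 0.5154)² / 0.09 = 20.1.
- With continuity correction: (20.1/4) × [1 + √(1 + 4/(20.1 × 0.30))]² = 26.4, so 27 per arm, or 54.
- Dropout: 54 / 0.90 = 60.

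The stated 54 and 60 reproduce. There is no stated biomarker power to reproduce.

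**2. Expected responders.** Arm 1: 0.15 × 30 = 4.5 (0.15 × 27 = 4.05 if 27 are evaluable). Arm 2: 0.45 × 30 = 13.5. Together 18. With Binomial(30, 0.15), the chance of 2 or fewer responders in Arm 1 is 15%, and of 3 or fewer 32%. The biomarker population is restricted to patients with available data, so 30 per arm is a ceiling.

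**3. Power under a graded association.** Assumptions not in the documents: biomarker and shrinkage are bivariate normal with correlation rho, and the test level is two-sided 0.05. Responders are the top 15% (Arm 1) or 45% (Arm 2) of shrinkage. The exact Wilcoxon test of responders v non-responders is compared with Spearman on the graded change, n = 30 per arm, 20,000 simulated trials per cell. Losses are in percentage points, taken before rounding.

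| rho | Arm 1 Wilcoxon | Arm 1 Spearman | Loss | Arm 2 Wilcoxon | Arm 2 Spearman | Loss |
|---|---|---|---|---|---|---|
| 0.2 | 9% | 17% | 8 | 13% | 17% | 5 |
| 0.3 | 16% | 33% | 18 | 23% | 33% | 10 |
| 0.4 | 26% | 55% | 29 | 38% | 55% | 17 |
| 0.5 | 38% | 77% | 39 | 58% | 77% | 19 |
| 0.6 | 55% | 92% | 38 | 78% | 93% | 15 |
| 0.7 | 70% | 99% | 29 | 92% | 99% | 7 |

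**4. Sensitivity, rho 0.3 to 0.6.**

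- Worst 15% of patients unscanned and tied at the worst rank (4,000 trials per cell): losses of 15, 30, 38 and 39 points in Arm 1, and 11, 16, 19 and 15 in Arm 2.
- Worst 30% unscanned: 17 to 38 points in Arm 1, 8 to 17 in Arm 2.
- Arm 1 with 27 patients: 15 to 40 points.
- 20% of would-be responders failing to qualify for reasons unrelated to the biomarker: 0.32 v 0.77 in Arm 1 at rho 0.5, so the gap does not shrink.

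**5. Pooled model.** With n = 60, about 18 responders and an arm term, logistic v linear power is 42% v 65%, 66% v 88% and 85% v 98% at rho 0.3, 0.4 and 0.5. The losses are 65 − 42 = 23, 88 − 66 = 22 and 98 − 85 = 13 points. These are approximate: 1,500 trials per cell, and some logistic fits did not converge.

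**6. The opposite case.** Let the biomarker be shifted in responders only, with no gradient within either group. At a 1 SD shift in Arm 1, the planned Wilcoxon has power of about 0.39 against 0.19 for Spearman. Over shifts of 0.8 to 2 SD it gains 14 to 43 points in Arm 1 and 2 to 14 in Arm 2.

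**The case against.** The strongest reply is that the planned analysis answers the stated question. Section 2.1 asks about response, and response here is composite. A new lesion is progression whatever the target lesions do (sections 12.1.7 and 12.1.9), non-target disease counts, and CR or PR must be confirmed (section 12.1.10). A patient with 35% shrinkage and a new lesion has progressed, yet would rank well on percent change. Some scans will be incompletely evaluated, so percent change will not exist for everyone. This stands: percent change is a related outcome, not a substitute, and it needs its own rules.

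The direction of the gain also depends on the shape of the association, which the documents cannot settle. Step 6 shows that the planned test can win by as much as it loses in step 3. A reader might infer that percent change should become the main biomarker analysis and the planned tests supportive. The evidence does not support that reordering; it supports having both.

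A reader might also infer that PD-L1 itself will be analysed only as positive or negative. Section 12.3.1 defines positivity and section 16.1 lists a status, but neither says the percentage is discarded, and a Wilcoxon test of laboratory measurements suits ungrouped values.

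Finally, these analyses are exploratory, carry no decision rule, and nothing in section 14.0 forbids a supplementary analysis. That is correct and limits the weight of the point.

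**Conclusion.** The point holds as a cheap improvement, not as an error in the plan. Section 14.0 uses only yes/no response for biomarkers while a graded measure is already collected, and the count of about 4 to 5 Arm 1 responders follows from the plan's own figures. For assumed rho of 0.3 to 0.6 at two-sided 0.05, the planned Wilcoxon test gives up about 15 to 39 points of power in Arm 1 and about 10 to 20 in Arm 2. The pooled logistic model gives up about 13 to 23 points at rho 0.3 to 0.5. The loss is smaller at rho 0.2, and the sign reverses if a biomarker acts only as a responder/non-responder switch.

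It would go too far to say that the change makes a null Arm 1 result informative. Spearman power there is still only about 33% at rho 0.3 and 55% at rho 0.4.

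**What to change.** Keep the Wilcoxon and logistic analyses in section 14.0 without demoting them, and add one pre-specified exploratory analysis:

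- **Outcome:** best percent change from baseline in the sum of non-irradiated target-lesion diameters, using scans up to first progression. This matches section 13.3, which excludes later responses from the primary endpoint.
- **Method:** a rank correlation with each biomarker within arm, and a rank-based linear model with an arm term.
- **Rules to state in advance:** worst rank for patients with no post-baseline scan because of death or clinical progression; a rule for patients with new lesions or non-target progression; and a rule for incompletely evaluated scans.
- **Interpretation:** a sentence saying that percent change is related to composite RECIST response but is not the same thing.
- **PD-L1:** where the assay supplies the percentage of stained tumour cells, analyse it ungrouped as well as by the 5% cut.

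The cost is some SAP wording and a little programming, plus a data field if the PD-L1 percentage is available and not already captured. No extra patients, scans or samples are needed. The downside is one more exploratory test per biomarker, which should be disclosed. The primary ORR endpoint and its analysis stay as they are.
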